## Objectives

List your research objectives. Please include a summary of intended research objectives in the box below.

To demonstrate whether four sessions of TBS improves attentional bias and craving in PLWHA smokers compared to four sessions of sham stimulation. We hypothesize 4 sessions of TBS to the left DLPFC will significantly improve attentional bias and craving for smoking cues compared to neutral cues in a population of subjects who are smokers with HIV/AIDS compared to sham stimulation.

## Study Design

Describe and explain the study design (e.g., observational, secondary analysis, single/double blind, parallel, crossover, deception, etc.).

- *Clinical Research:* Indicate whether subjects will be randomized and whether subjects will receive any placebo.

- **Community-Based Participatory Research:** If you are conducting [community-based participatory research \(CBPR\)](#), describe strategies for involvement of community members in the design and implementation of the study, and dissemination of results from the study.
- **Qualitative research:** Indicate ranges where flexibility is needed, if a fixed interview transcript is not available, describe interview topics including the most sensitive potential questions.
- **Research Repositories:** If the purpose of this submission is to establish a Research Repository (bank, registry) and the material you plan to collect is already available from a commercial supplier, clinical lab, or established IRB approved research repository, provide scientific justification for establishing an additional repository collecting duplicate material. Describe the repository design and operating procedures. For relevant information to include, see the [UK Research Biospecimen Bank Guidance](#) or the [UK Research Registry Guidance](#).

This will be a crossover randomized controlled trial. Recruitment for the study will be done by research assistant and/or principal investigator. All subjects will receive both TBS and sham stimulation in a randomized manner with counterbalancing. Subjects will be randomized to two groups - one group that receives actual TBS first and sham TMS later, the other group receiving sham TMS first and TBS later. The PI ([name]) will be blind to the randomization status and will supervise the TMS session. The PI will remain blind to the randomization status. Subjects will also remain blind to the randomization status. This will be facilitated by the Magventure Active/sham TMS coil which has been shown to maintain integrity of blinding in subjects regarding group assignment. We will recruit 30 subjects in each arm (2 arms – TBS and sham, total n=60), subjects will be randomized to one of these arms using a computer-generated randomization protocol.

On day one of the study, we will perform baseline assessments including breath alcohol level, opioid and tobacco craving questionnaires, smoking attentional bias tasks using eye tracker, inhibitory control and delay discounting tasks, collection of baseline demographics, vital signs (including heart rate, systolic and diastolic blood pressures), Snaith Hamilton Pleasure Scale and Hamilton depression rating scale. All of these baseline assessments will take a total of three hours. We will also obtain resting and active motor threshold from the first dorsal interosseous (FDI) muscle. Following this subjects will be transported to Magnetic Resonance Imaging and Spectroscopy Center (MRISC), affiliated with University of Kentucky for collection of their baseline MRI brain scan that will last thirty minutes. Subjects will also be escorted to the MRISC at the UK Medical Center by the PI ([name]) and a research assistant. Subsequently, neuroimaging data (MRI brain) will be acquired using a Siemens 3-Tesla (3T) PRISMA MRI scanner as described under Data Collection below.

On day two of the study will be the TMS session. We have two groups in this study, and you may be assigned to the actual TMS group or placebo by chance. If you are assigned to the actual TMS group, you will receive the intended experimental method of stimulation and dosing. The TMS paradigm we use is called theta burst stimulation (TBS) which is short and efficient TMS stimulation method. In this group, you will receive four sessions of actual TBS. In the placebo group, you will receive a different kind of stimulation which mimics the actual experimental one but does not deliver any electricity to the brain. This is called sham TMS and you will receive four sessions of it. In both groups, sessions will be separated by 50 minutes and during this time, you will perform a visual attention and a few scales to measure your craving for opioids and cigarettes. On day two we will also have you perform a stress test to assess craving for opioids and cigarettes. This would involve immersing your feet in cold water for three minutes while performing a number recall task. This will help us measure your craving for opioids and cigarettes more accurately than just doing the scales. At the end of day two, we will obtain an MRI brain scan.

This section will attach a schedule and lists of tasks that need to complete for four visits.

(Figure 1) will be attached to this section, incorporating all four visits details tasks. Timeline Tasks

#### Attachments

Attach Type	File Name
StudyDesign	(Figure 1) Timeline Tasks for four visits.docx
StudyDesign	Day_1_timeline_tasks.png
StudyDesign	Day_2_timeline_tasks.png
StudyDesign	Day3_timeline_tasks.png

#### Subject Recruitment Methods & Advertising

Describe how the study team will identify and recruit subjects. Please consider the following items and provide additional information as needed so that the IRB can follow each step of the recruitment process.

- How will the study team identify potential participants?
- Who will first contact the potential subjects, and how?
- Will you use advertisements? If so, how will you distribute those?
- How and where will the research team meet with potential participants?
- If applicable, describe proposed outreach programs for recruiting women, minorities, or disparate populations.
- How you will minimize undue influence in recruitment?
- Attach copies of all recruiting and advertising materials (emails, verbal scripts, flyers, posts, messages, etc.).

For additional information on recruiting and advertising:

- [IRB Application Instructions - Advertisements](#)
- [PI Guide to Identification and Recruitment of Human Subjects for Research](#)

We will recruit 60 subjects from the Bluegrass Care Clinic, SMART clinic and Beyond Birth Clinic. Study members will interface with all providers in these clinics on a daily basis. All providers in these clinics will be provided multiple copies of the business cards. All providers in these clinics will also be informed about inclusion and exclusion criteria for the study, based on which all patients will be screened by them. Initial contact will be made with potential subjects by those having legitimate access to the subjects' identities/information (ie only providers in the clinic). The PI ([name]) and a research assistant will interface with a contact in each of these clinics on a daily basis. Business cards (that list a few study details and a call back number if subjects are interested in the study) will be provided to subjects at each of these clinics by clinic providers. The case manager for this clinic [name] will send an email to all patients from the Bluegrass Care Clinic, with the business card attached and informing them about the study. A draft of the email is attached in the research procedure section. Subjects interested in the study can call the number provided on the business card to express interest in the study. This number belongs to the Patient Oriented and Population Science Shared Resource Facility (POP SRF). The POP SRF headed by [name] will help the study team with phone screening subjects for the study and their recruitment if they fulfill inclusion and exclusion criteria. Members of the POP SRF ([name], [name] and [name]) have also been added to the list of key study personnel. The POP SRF works closely with Markey Cancer Center and they will assist the PI with recruitment. We are able to avail of this assistance since the study is funded by a pilot cancer center grant from Markey Cancer Center (MCC). Once a subject is identified as suitable for the study, the POP SRF will inform [name] via UK email. Subjects will be asked to meet [name]/research assistant either at MRISC or at [name] to get informed consent if they are interested in study participation and fulfill other eligibility criteria for the study. All data collected from phone screening would be entered into RedCap, regardless of whether subjects do or don't fulfill inclusion and exclusion criteria. During screening, subjects will not be coerced to participate in any way.

We have submitted an application to obtain a certificate Certificate of Confidentiality (CoC) for this study.

We will provide business cards having the study info to potential study subjects. This business card will display the contact number for the Patient Oriented and

Population Science Shared Resource Facility (POP SRF) [name] who will be involved in study recruitment.

To increase the UK clinic enrollment rate, we submit a stamped flyer by the CCTS for the UK-E-IRB review and approval.

**Attachments**

Attach Type	File Name
Advertising	70889-Updated Flyer-June-14-2022-STAMPED.pdf
Advertising	70889_business_card PR STAMPED.pdf

## Research Procedures

Describe how the research will be conducted.

- What experience will study participants have?
- What will study participants be expected to do?
- How long will the study last?
- Outline the schedule and timing of study procedures.
- Provide visit-by-visit listing of all procedures that will take place.
- Identify all procedures that will be carried out with each group of participants.
- Describe deception and debrief procedures if deception is involved.

Differentiate between procedures that involve standard/routine clinical care and those that will be performed specifically for this research project. List medications that are explicitly forbidden or permitted during study participation.

On day one of the study, following informed consent, we will perform baseline assessments including breath alcohol level, opioid and tobacco craving questionnaires, smoking attentional bias tasks using eye tracker, inhibitory control and delay discounting tasks, collection of baseline demographics, vital signs (including heart rate, systolic and diastolic blood pressures), Snaith Hamilton Pleasure Scale and Hamilton depression rating scale. All of these baseline assessments will take a total of three hours. We will also obtain resting and active motor threshold from the first dorsal interosseous (FDI) muscle. Following this subjects will be transported to Magnetic Resonance Imaging and Spectroscopy Center (MRISC), affiliated with University of Kentucky for collection of their baseline MRI brain scan that will last thirty minutes. Subjects will also be escorted to the MRISC at the UK Medical Center by the PI ([name]) and a research assistant. Subsequently, neuroimaging data (MRI brain) will be acquired using a Siemens 3-Tesla (3T) PRISMA MRI scanner as described under Data Collection below. On the second and third days, subjects will receive either four sessions of active TBS or four sessions of sham stimulation. Subjects will receive all four sessions of either TBS or sham on one particular day, all four sessions will be the same in dosing and will be delivered at an interval of fifty minutes each. Each session will last ten minutes regardless of it being TBS or sham. Sessions will be delivered 120% resting motor threshold (RMT) to the left dorsolateral prefrontal cortex using a figure 8 coil and MagVenture MagPro x100 device (MagVenture A/S, Denmark), with TMS coil position stabilized using BrainSight (Rogue Solutions, Montreal, Canada). Deciding who will get TBS/sham sessions on day two will be done in a randomized manner with counterbalancing. Along with the stimulation, subjects will also perform a host of other tasks as shown in figures 1. Craving for cigarettes will be measured while performing a stress induction procedure involving immersion of feet in cold water coupled with performing a working memory task (cold pressor test and PASAT as described below). The figures also indicate the timing of these tasks. At the end of the stimulation sessions and tasks, post session MRI brain scans will be collected and subjects will be dispersed payments for the respective days.

On day two of the study will be the TMS session. We have two groups in this study, and you may be assigned to the actual TMS group or placebo by chance. If you are assigned to the actual TMS group, you will receive the intended experimental method of stimulation and dosing. The TMS paradigm we use is called theta burst stimulation (TBS) which is short and efficient TMS stimulation method. In this group, you will receive four sessions of actual TBS. In the placebo group, you will receive a different kind of stimulation which mimics the actual experimental one but does not deliver any electricity to the brain. This is called sham TMS and you will receive four sessions of it. In both groups, sessions will be separated by 50 minutes and during this time, you will perform a visual attention and a few scales to measure your craving for opioids and cigarettes. On day two we will also have you perform a stress test to assess craving for opioids and cigarettes. This would involve immersing your feet in cold water for three minutes while performing a number recall task. This will help us measure your craving for opioids and cigarettes more accurately than just doing the scales. At the end of day two, we will obtain an MRI brain scan.

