### Motor Threshold

Motor threshold (MT) is defined as the TMS pulse amplitude needed to elicit an EMG response of 50  $\mu$ V peak-to-peak average amplitude in a target muscle. MT is the standard in the field for determining the intensity of TMS for everyone to reduce seizure risk. The MEP for the right first dorsal interosseus (FDI) will be measured with EMG. The scalp region producing the largest amplitude MEP will be identified. At that scalp location, we will determine the TMS intensity eliciting average MEP amplitude of 50  $\mu$ V peak-to- peak in the first DI muscle using an amplitude titration procedure (at least 5/10 trials). Individual MT will be used to determine the intensity of theta burst stimulation for everyone, as recommended by safety guidelines.

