### TBS application

A magnetic coil will be placed on the scalp and held in place with frameless stereotaxic equipment, using a sophisticated method of coil placement that will coregister scalp positions directly onto an average brain template. This Frameless Stereotaxic System Brainsight offers real-time three-dimensional display of cortical localization as the TMS coil is moved across the scalp. This will be used for coil positioning. This system uses a programmed robot arm to precisely position the TMS coil, and maintain its position, within 1 mm of the brain target chosen. Earplugs will be worn to protect hearing and low-volume white noise will be played through TMS-compatible headphones to mask the sound of the coil clicks. The intensity of the stimulation will be 80% of active motor threshold as reported in a previous studies. The participant will be seated comfortably with headphones and earplugs to protect the subject's hearing.

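### The stimulation intensity is given both as 120% of resting motor threshold and as 80% of active motor threshold, so the dose of the tested intervention is not defined

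*Combined protocol and SAP*

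**What the plan says.** The day-by-day account in Research Procedures states: "Sessions will be delivered 120% resting motor threshold (RMT) to the left dorsolateral prefrontal cortex using a figure 8 coil". It also says of the sessions given on one day that "all four sessions will be the same in dosing and will be delivered at an interval of fifty minutes each".

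The TBS application subsection, within the same Research Procedures section, states: "The intensity of the stimulation will be 80% of active motor threshold as reported in a previous studies".

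The Motor Threshold subsection lies between them and is meant to link threshold to dose: "Individual MT will be used to determine the intensity of theta burst stimulation for everyone, as recommended by safety guidelines". It describes one titration, to a 50 µV average response in at least 5 of 10 trials. It does not say whether the muscle is relaxed or contracting. The day-one assessments include both measurements: "We will also obtain resting and active motor threshold from the first dorsal interosseous (FDI) muscle".

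The Objectives section gives no intensity for the intervention: "We hypothesize 4 sessions of TBS to the left DLPFC will significantly improve attentional bias and craving".

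**The concern.** Both statements are written as this study's own intensity, and they cannot both be right. A percentage of resting threshold and a percentage of active threshold are different scales, and here the percentages differ as well.

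Three things are at stake.

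- **Attribution.** The Background presents adequate dosing as part of the rationale and says the results will support a grant resubmission. With two intensities in the plan, neither a positive nor a null result can be assigned to a reproducible dose from the text.
- **Variability.** If different participants were treated under different rules, the active condition would mix doses under one label. Four participants are enrolled, so one of them supplies at least a quarter of the active-condition participants.
- **Safety.** The Motor Threshold subsection links threshold-based intensity to reducing seizure risk, and the risk section undertakes to follow guideline limits on intensity. A reader holding those guidelines would not know which of the two intensities to compare with them.

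**Working it through.** The plan offers no figure to reproduce. The check is a comparison of texts, followed by one ratio to show the size of the gap.

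**Can the two statements be read together?**

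1. *Different sessions at different intensities.* Excluded, because Research Procedures says the four sessions have the same dosing.
2. *Different arms or days.* Neither statement carries such a limit.
3. *Only one rule is feasible.* Excluded, because resting and active thresholds are both obtained on day one.
4. *The Motor Threshold subsection decides.* It does not. It refers to an individual threshold without naming it as resting or active.
5. *A later change resolved it.* The modification texts under Research Procedures, Data Collection & Research Materials and Payment cover follow-up visits, cotinine and carbon monoxide tests, heart rate recording, blood samples and payments. None mentions intensity.

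**How far apart are they?**

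Inputs from the documents: 1.20 × RMT (Research Procedures) and 0.80 × AMT (TBS application). Write r = AMT/RMT. The documents give no value for r, so the values below are assumptions.

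Ratio of the two intensities = (1.20 × RMT) / (0.80 × AMT) = 1.5 / r.

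The second rule expressed on the resting scale = 80% × r.

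| Assumed r | 80% AMT as % of RMT | 120% RMT ÷ 80% AMT |
|---|---|---|
| 1.0 | 80 | 1.50 |
| 0.9 | 72 | 1.67 |
| 0.8 | 64 | 1.88 |
| 0.7 | 56 | 2.14 |
| 0.6 | 48 | 2.50 |

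The rules coincide when 1.5 / r = 1, that is, when AMT is 1.5 times RMT. If active threshold does not exceed resting threshold (r ≤ 1), the first rule is always at least 50% more intense than the second. That is too large for a rounding or unit difference.

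**The case against.** The contradiction itself is hard to dispute. The best opposing case concerns its reach.

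- *Much of the intervention is defined.* Target, coil, device, number of sessions, session length and interval are all stated. This is correct: the finding is about intensity. But intensity is the dose, and the rest of the definition does not supply it.
- *Mixed dosing is not shown.* One investigator supervises the stimulation, four people were enrolled, and the study is closed to enrolment with data under analysis. A single setting used throughout is quite plausible. If so, no variance was added, and disclosing the setting would restore attribution. This stands: the variance consequence is a possibility. The text still does not say which setting it was.
- *Guideline compliance could not be checked here anyway,* because the numerical limits sit in a cited source. This also stands in part. The conflict is not the only obstacle, but it would remain for a reader who has that source.
- *The ratios are illustrative.* Agreed. They rest on assumed values of r, and the finding does not depend on them.
- *Attachments not shown,* such as the timeline figures and the Study Device Form, may state an intensity. They might reveal what was used, but they would not remove the conflict in the current text.

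**Conclusion.** The concern holds. The current text states two incompatible rules for the dose of the tested intervention, and nothing in it says which governs. The gap is at least 1.5-fold if active threshold does not exceed resting threshold, and 1.67 to 2.14-fold for assumed AMT/RMT ratios of 0.9 to 0.7. The contradiction follows from the text alone; only its size rests on those assumptions. Whether participants actually received different intensities cannot be known from the documents. This must be corrected before results are reported, because no finding can otherwise be linked to a stated dose. No view is taken on which intensity is right.

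**What to change.** 1. Reconcile the Research Procedures account, the Motor Threshold subsection and the TBS application subsection, so that one intensity on one named threshold appears throughout. The investigators must confirm which applies.
2. Make the threshold procedure match that choice, stating whether the target muscle is at rest or contracting.
3. Since treatment is over, retrieve from session logs each participant's delivered intensity (percent of stimulator output) and both measured thresholds. Report results with these values, and say plainly if they were not recorded.
4. If the logs show that more than one rule was used, state who was treated under which rule.

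The cost is a wording amendment and a search of the logs for four participants. The unknown is whether the settings were kept.

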### Motor Threshold

Motor threshold (MT) is defined as the TMS pulse amplitude needed to elicit an EMG response of 50  $\mu$ V peak-to-peak average amplitude in a target muscle. MT is the standard in the field for determining the intensity of TMS for everyone to reduce seizure risk. The MEP for the right first dorsal interosseus (FDI) will be measured with EMG. The scalp region producing the largest amplitude MEP will be identified. At that scalp location, we will determine the TMS intensity eliciting average MEP amplitude of 50  $\mu$ V peak-to- peak in the first DI muscle using an amplitude titration procedure (at least 5/10 trials). Individual MT will be used to determine the intensity of theta burst stimulation for everyone, as recommended by safety guidelines.

### TBS application

A magnetic coil will be placed on the scalp and held in place with frameless stereotaxic equipment, using a sophisticated method of coil placement that will coregister scalp positions directly onto an average brain template. This Frameless Stereotaxic System Brainsight offers real-time three-dimensional display of cortical localization as the TMS coil is moved across the scalp. This will be used for coil positioning. This system uses a programmed robot arm to precisely position the TMS coil, and maintain its position, within 1 mm of the brain target chosen. Earplugs will be worn to protect hearing and low-volume white noise will be played through TMS-compatible headphones to mask the sound of the coil clicks. The intensity of the stimulation will be 80% of active motor threshold as reported in a previous studies. The participant will be seated comfortably with headphones and earplugs to protect the subject's hearing.

